Since conservative treatment is not always effective,^{1,20} rotator cuff repairs are commonly used surgical procedures^{1,4,25,26,10,15,17,20-24} and a procedure that is becoming more frequent in advanced ages.^{22,27}

Rehabilitation plays an essential role in the recovery of rotator cuff repair,^{8–10,13,15,20,28–31} and should be customized to the patients characteristics and needs.^{15,18,20,32} Different aspects must be taken into consideration for functional recovery, such as age, activity levels, extent and location of the tear, duration of symptoms, prior muscle atrophy or fatty infiltration and concomitant pathologies.^{10,17,20,23,24,31,33}

The primary goal of the rehabilitation is to relieve pain, restore function, range of motion, strength,^{4,20,29,31,34–36} balancing the need of protecting the repair and the need of mobilization to avoid stiffness and restore normal function and kinematics.^{15,20,30,31,37,38} This balance, however, is very delicate, as re-tears or failed healing are very common after surgery^{22,25,27,39}, and therefore therapies must focus on improving function without compromising the healing process.^{15,27,31}

Assure an early passive range of motion is recommended by many authors to prevent stiffness, one of the most frequent complications after rotator cuff repairs^{15,37,38,40–42} as well as joint adhesions and further tendon degradation. Conversely, longer immobilization periods can promote tendon healing and reduce the rates of re-tear.^{32,37,38,43} There is no consensus on this matter, with an immobilization period of 6 weeks being the most common period advised.^{20,28} However, several studies found no differences between them in function, pain, ROM or re-tears ratio, concluding that early mobilization may be beneficial.^{22,23,28,30,34,37,38,40,41} Furthermore, some studies demonstrate that early initiation of rehabilitation with active exercise does not appear to affect patient-reported pain and disability outcomes in a short (≤ 3 months), mid (6

SH-RCT-ARCR-01 Study Protocol

months) or long-term period (≥ 12 months).^{8,9,36} Still, even within the early mobilization group, there is no consensus on how early should the mobilization begin - since day one to 2 days after, 1 week after, 5 weeks after.^{4,28,41}

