5.2 Secondary outcomes

The secondary outcomes will be:

- The change in patient reported function in comparison to the baseline, measured by the QuickDASH score
- The change in shoulder range of motion in comparison to the baseline, measured by the shoulder flexion degree in a sitting position (in degrees)

6. Sample size estimate

Sample size estimation was performed taking into consideration the primary outcome measure – The Constant Score - and a non-inferiority scenario.

In the absence of similar studies, the calculations were made taking into account the study by Arndt *et al.* (2012)⁴⁰. This was a large study (n=100 patients) which compared two different rehabilitation protocols after ARCR and which used the same primary outcome as our study. In this study, the standard deviation of the Constant

Score at baseline was 12.0. A Minimal Clinically Important Difference (MCID) of 10.4 was considered, based on the study by Constant *et al.* (2008).⁵⁵

Considering a power of 90%, a two-sided 0.05 significance level and a 10% dropout rate, 68 patients would be necessary to detect a 10.4 points difference between the two groups.

7. Location of Recruitment

Patients will be recruited at Hospital da Prelada - [name] da Cruz.

8. Inclusion criteria

- a) Patients over 18 and under 70 years old
- b) Shoulder pain and functional limitation with clinical examination compatible with reparable rotator cuff tear
- c) Imaging (MRI or ultrasound) evidence of rotator cuff tear (supra and/or infraspinatus tendon tear inferior to 5cm)
- d) Indication for a rotator cuff repair according to the patient's orthopedic surgeon
- e) Ability to understand simple and complex motor commands
- f) Availability of a carer to assist the patient after surgery

9. Exclusion criteria

Preoperative

- a) Patients with indication for revision cuff repair
- b) Complex cuff tears (involving subscapularis tendon or more than one tendon besides supra and infraspinatus, or massive dimension tears)

- c) Glenohumeral arthritis
- d) Irreparable tendon defect
- e) Patients with concomitant neurological disorders (ex. Stroke, Parkinson's disease, multiple sclerosis)
- f) Aphasia, dementia or psychiatric comorbidity interfering with the communication or compliance to the rehabilitation process
- g) Respiratory, cardiac, metabolic conditions or others incompatible with at least 30 minutes of light to moderate physical activity

Postoperative

- h) Irreparable tendon lesion

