- i) Major medical complications occurring after surgery that prevent the discharge of the patient within 5 days after surgery
- j) Other medical and/or surgical complications that prevent the patient from complying with a rehabilitation program
- k) Blind and/or illiterate patients

10. Methods for identifying and recruiting patients

All patients admitted for rotator cuff repair during the study period will be screened for inclusion and exclusion criteria.

When a potential candidate is identified, the local investigator will approach the candidate and explain the study in detail. The prospective candidate will be given the patient information document and sufficient time to consider whether he wishes to participate in the study.

Subsequently, the prospective candidate will be given opportunity to clarify any

doubts, after which the informed consent form will be signed and dated in duplicate by the patient and the investigator. Only then will the randomization and baseline assessments be performed.

11. Patient allocation to study groups

For logistic reasons, the study will be restricted to patients living in a 20km radius around the investigation center. Patient allocation to the two groups will be performed in a random way, in a 1:1 ratio in blocks of six. This will be done using an online randomizer (<https://www.randomizer.org>).

The allocation of patients to each group will be performed centrally by one investigator - [name] - and communicated to the responsible for data acquisition only after patient enrollment. This investigator will not be involved in data collection or in outcomes assessment.

12. Blinding

The nature of the study does not allow blinding of the patients regarding study groups. However, participants will be blinded to the primary and secondary outcomes being measured. All patient assessments will be performed by an investigator blinded for randomization groups. Statistical analysis will be performed blinded for randomization group.

13. Patient assessment

Patients will be assessed pre-operatively, and then at 6, 12, 16 and 20 weeks after the surgery. In patients where a decision is made to extend the program to 24 weeks,

another assessment will be made at this point. An assessment will also be made at 12 months after surgery.

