13.1 Baseline assessment

Participant characterization will consist of:

- a) Demographics (gender, date of birth);
- b) Educational level (years);
- c) Affected side
- d) Injured structures
- e) Size of tear
- f) Date of surgery
- g) Comorbidities
 - a. Factors affecting tissue healing: Smoking, Diabetes, Steroid intake
 - b. Other disorders: cardiac, respiratory, hypertension
 - c. Time between diagnosis and surgery
- h) Body Mass Index
- i) Constant score
- j) QuickDASH
- k) Shoulder range of motion

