Patients in the active comparator group will receive face-to-face rehabilitation sessions provided by a physical therapist. Therefore, patient safety will be ensured at all times during the sessions. Patients will be able to report adverse events to their physical therapist. Moreover, the patient's orthopedic surgeon will be notified in case of detrimental clinical progression, so that the patient can be re-evaluated.

For patients in the experimental group, safety of the remote sessions will be evaluated through pain and fatigue scores (graduated from 0 to 10) collected at the end of each session. These will be presented to the patient using the mobile App and will be available for remote monitoring by their physical therapist. In case of excessive pain or fatigue, patients will be contacted by their physical therapist to ascertain the cause and change prescription if needed. Patients will also be asked to report any other adverse events to their physical therapist by telephone. Moreover, the patient's orthopedic surgeon will be notified in case of detrimental clinical progression, so that the patient can be re-evaluated.

The adverse events will be registered in the patient's file (beginning date, resolution date (if applicable), resolution state, severity).

16. Statistical analysis

To assess differences in clinical and demographic variables of the patients allocated to the two study groups, independent samples t test or Mann-Whitney U test will be used for quantitative variables. For qualitative variables, Chi-squared test or Fisher's exact test will be used.

Outcome analysis will be performed using a per-protocol analysis. The impact of the interventions in the primary and secondary outcomes will be evaluated considering

the change between baseline and week 20. Differences between the two study groups will be performed using independent samples t test or Mann-Whitney U test.

Since outcomes will be measured in several different times during the rehabilitation program, a repeated measures analysis will also be performed, using a 3x2 ANOVA with group as an independent factor and time as a within-subjects factor.

17. Potential Risks and Benefits to Participants

There are no invasive procedures involved in this research protocol and, given the nature of the intervention, no relevant risks are foreseen.

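### Age and tear size are recorded before treatment but used neither in the randomisation nor in the outcome analysis, which gives up some precision; the planned baseline significance tests do not make up for it

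*Combined protocol and SAP*

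**What the plan says.** The background states: "Different aspects must be taken into consideration for functional recovery, such as age, activity levels, extent and location of the tear, duration of symptoms". It goes on to name muscle atrophy or fatty infiltration and concomitant pathologies.

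Eligibility leaves room for both age and tear size to vary. Section 8 admits "Patients over 18 and under 70 years old" with a "supra and/or infraspinatus tendon tear inferior to 5cm" shown on MRI or ultrasound. Section 13.1 records age through "Demographics (gender, date of birth" and lists tear size as a separate item.

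Section 11 says: "Patient allocation to the two groups will be performed in a random way, in a 1:1 ratio in blocks of six". No stratification factor is named. Section 10 places randomisation after consent, alongside the baseline assessments: "Only then will the randomization and baseline assessments be performed".

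Section 16 opens with between-arm tests of baseline variables, whose purpose it gives as "To assess differences in clinical and demographic variables of the patients allocated to the two study groups": t or Mann-Whitney for quantitative variables, chi-squared or Fisher for qualitative ones. It attaches no consequence to the results. The outcome analysis is per-protocol. It uses a two-sample t or Mann-Whitney test on change from baseline to week 20, plus a repeated-measures ANOVA with group and time as its only factors. No covariate appears anywhere in the plan.

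**The concern.** Blocks of six keep the numbers per arm equal. They do nothing to balance age or tear size. With about 30 evaluable patients per arm, either factor can differ between arms by chance, and an unadjusted test leaves that difference in the estimate. It also leaves in the residual error whatever outcome variation the two factors explain.

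The baseline tests do not fill the gap. Among randomised patients, any baseline difference is due to chance, so a p-value answers a question whose answer is already known. Whether an imbalance matters depends on its size and on how strongly the factor predicts outcome. The p-value measures neither.

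At stake are a modest amount of precision and, in a trial that happens to be imbalanced, an estimate that is harder to defend. A baseline p-value below 0.05 could also prompt an adjustment chosen after the data are seen. This point is separate from how the baseline Constant Score itself is handled.

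**Working it through.** **Inputs from the documents.** Section 6: SD 12.0 (Constant Score at baseline), difference 10.4, two-sided alpha 0.05, power 90%, dropout 10%, N = 68. Section 11: 1:1 allocation.

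**Assumptions, not in the documents.** The SD of the week-20 change is taken as 12. The share of outcome variance explained by age and tear size together (R²) is taken as 5% to 20%.

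**1. The plan's own sample size.** n per arm = 2 × 12² × (1.960 + 1.282)² / 10.4² = 2 × 144 × 10.507 / 108.16 = 27.98, so 28. Dividing by 0.9 gives 32 per arm, total 64. A t-based calculation gives 29 per arm, then 33, total 66. Allowing for Mann-Whitney efficiency, 28 / 0.955 gives 30 per arm, and 30 / 0.9 gives 34, total 68. The stated N is reproduced. After 10% dropout, 68 × 0.9 = 61.2, or about 30 evaluable per arm.

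**2. Precision.** Unadjusted SE = 12 × √(2/30) = 3.10. Adjusted SE = 3.10 × √(1 − R²). Power is for 10.4 points, by normal approximation.

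| R² | SE (points) | Power |
|---|---|---|
| 0 | 3.10 | 91.9% |
| 0.05 | 3.02 | 93.1% |
| 0.10 | 2.94 | 94.3% |
| 0.20 | 2.77 | 96.3% |

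This formula ignores the cost of estimating the coefficients. With k = 2 covariates and N = 60, the SE is multiplied by √(1 + k/(N − k − 3)) = √(1 + 2/55) = 1.018. The range then becomes 3.07 (R² 0.05) to 2.82 (R² 0.20). At the low end, most of the gain is lost.

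**3. Chance imbalance.** The standardised difference between arms in a continuous covariate has SD √(2/30) = 0.258. A difference above 0.25 SD therefore arises in 33% of trials, and one above 0.5 SD in 5%. The shift in the treatment difference is √R² × 12 × imbalance, treating the two factors as one combined predictor:
- 0.25 SD: from 0.224 × 12 × 0.25 = 0.7 to 0.447 × 12 × 0.25 = 1.3 points
- 0.5 SD: 1.3 to 2.7 points

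**4. Type I error.** In 40,000 simulated trials at 30 per arm, with one covariate correlated 0.3 or 0.5 with outcome, overall type I error was 5.1% and 5.3% unadjusted, and 5.1% adjusted in both cases. About 7% of trials had an imbalance above 0.4 SD together with a non-significant baseline test. In those, the unadjusted rate was 6.7% (correlation 0.3) or 10.8% (0.5), against 4.8% to 4.9% adjusted.

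**5. What the baseline tests do.** Take a realised split of 18/30 against 12/30, which is 20 percentage points. z = 0.20 / √(0.25 × 2/30) = 1.55, so p = 0.12 by uncorrected chi-squared; Fisher's exact test gives 0.20. Neither flags it.

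In the other direction, the list in Section 13.1, leaving out date of surgery, has 14 items before the outcome measures and 17 with each outcome measure counted once. Taking 12 to 18 independent tests, the chance of at least one p < 0.05 under correct randomisation is 1 − 0.95¹² = 46% to 1 − 0.95¹⁸ = 60%. The items are correlated (the Constant Score itself contains range of motion) and Fisher's test is conservative, so these are closer to upper limits.

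**The case against.** An unadjusted comparison of randomised arms is a legitimate analysis. Its standard error already allows for chance imbalance, its type I error is about 5% overall, and on the plan's own assumptions power is already about 92%. All of this stands, and it makes the point an efficiency gain rather than a correction of an invalid test. The raised error rates in step 4 apply to a small share of trials and to assumed correlations.

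A reader might infer more than the documents support in four ways.

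- **That the background commits the trial to adjust for these factors.** The sentence follows one about customising rehabilitation to the patient, and Section 14 takes up that theme. It says nothing about analysis, and it names other factors as well. It supports only the view that the authors regard age and tear extent as relevant to recovery.
- **That the baseline tests are the plan's safeguard for the comparison.** Section 16 gives them no such role and no decision rule.
- **That these tests have some probability of detecting a 60% against 40% split.** A power calculation would treat the split as a difference between populations, which randomisation rules out. A realised 18/30 against 12/30 has one fixed p-value and is not flagged.
- **That an imbalance could use up a large part of the 10.4 points.** That needs a strong prognostic effect, and the documents give none. Section 9 also narrows the range of tears by excluding massive, irreparable and revision cases.

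Because the analysis is per-protocol, exclusions after randomisation could produce imbalance that is not due to chance. Adjustment would reduce that only in part; it is a separate matter.

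**Conclusion.** The point holds as a matter of precision and prespecification. The plan leaves two recorded, plausibly prognostic variables out of both the randomisation and the analysis, and the only use it states for such baseline variables is in tests that cannot inform the comparison. The randomised comparison is not biased on average, and the sample size does not need to change.

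The size is modest: an SE of about 3.10 falling to between 3.02 and 2.77 points, or 3.07 to 2.82 after the cost of estimation. This rests on an SD of 12, which the documents give only for baseline scores, and on R² of 5% to 20%, which they do not give. At the low end the case for adjustment rests mainly on protection against chance imbalance; at the high end the precision gain is also worthwhile. The change is recommended because it costs almost nothing.

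**What to change.** Before any outcome data are seen, amend Section 16 as follows.

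1. Prespecify a linear model for the primary outcome and for each secondary outcome, with arm, the baseline value of that outcome, age (continuous) and tear size as fixed covariates. Use it whatever the baseline table shows. The baseline value belongs in the model: age and tear size alone would leave out an obvious covariate.
2. Define tear size as the preoperative imaging measurement, which eligibility already requires, and state its form in the model (continuous or grouped). Section 13.1 does not say whether the recorded size comes from imaging or from surgery. A covariate should precede allocation.
3. Replace the baseline p-values with descriptive summaries by arm.

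The cost is SAP wording and a few degrees of freedom: three if each covariate enters as one linear term, so with 60 patients the residual degrees of freedom fall from 58 to 55. The data are already being collected.

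Stratifying the allocation list on imaging tear size is optional, and only if recruitment has not started.

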The conventional rehabilitation group will receive home-based rehabilitation provided by a physiotherapist, 3 times a week, for 1 hour. Patients will also be instructed to perform additional unsupervised sessions in at least two other days of the week. Compliance to these additional sessions is not mandatory, but patients will be asked to fill in a diary regarding these extra-sessions.

The intervention arm, additionally to the one-to-one sessions, will perform daily home-based rehabilitation sessions using the system alone, under remote monitoring

SH-RCT-ARCR-01 Study Protocol

by a physiotherapist. Patients will be instructed to perform exercise sessions at least 5 times per week, but compliance to that frequency is not mandatory per protocol. The number of sessions, daily adherence and total training time will be registered automatically by the system and will be made available through the Web Portal, from where it can be transcribed to each patient file. When required, additional visits or telephone calls for technical assistance can be performed by the physical therapist. These will be registered as such in the patient file.

In the absence of a gold standard, the rehabilitation protocols were designed taking into account: a) a recent systematic review on the subject;⁴ b) a review of the concepts and evidence-based guidelines on this subject by van der Meijden *et al.* (2012)¹⁵; c) an overview of systematic reviews comparing early and conservative rehabilitation²⁸ and d) the protocol of the Massachusetts General Hospital for rehabilitation after rotator cuff repair.

The rehabilitation program will be based on the principles outlined in the following tables 1-4. In any case, these protocols can be tailored to the patient's specific needs, according to the assessment of the orthopedic surgeon and the physical therapist.

Table 1. Immediate Post-op Phase

Rotator cuff repair program: Immediate Post-op Phase (weeks 0 to 2) - Immobilization period	
Goals	Precautions
Control pain and swelling	
Protect the rotator cuff repair	Do not lift the operated arm
Protect wound healing	
Prevent shoulder stiffness	
Intervention	
Conventional PT group	Experimental Group
Use of a sling during the day and during the night until week 4	
Ice pack application to the operated shoulder for 15 minutes if necessary to reduce pain and swelling several times per day	
Promote the active movement of fingers, hand and elbow to increase circulation	

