Continue as above and progressively add: - Shoulder Abduction to full ROM Theraband exercises: - Standing external rotation (at 0° abduction) - Standing internal rotation (at 90°) - Standing shoulder flexion - Standing forward punch - Standing dynamic hug - Standing W's (external rotation with elbow flexion) - Standing Biceps curls - Seated row Dynamic strengthening exercises (first weeks limit resistance to max 1,5 to 2,5 kg): - Scapulohumeral rhythm exercises - Side-lying external rotation at 0° - Prone row, Scaption "Y", Extension - Standing forward flexion 1,5-2kg (scaption) - Standing external rotation at 90° abduction	Intervention of the Control Group + SWORD Phoenix exercises (adding Theraband or weight): - Scapula Elevation - Scapula Protraction - Scapula Retraction - Shoulder Flexion - Shoulder External Rotation - Shoulder Internal Rotation - Shoulder Abduction - Shoulder Horizontal Abduction - Seated Press-up - Push-up against a wall - Diagonals to flexion - Arm circles with 90° flexion - Arm circles with 90° abduction

Note: * may be less if patient is progressing well

The rehabilitation program may be extended until 24 weeks, according to the orthopaedic surgeon assessment.

Version 2.0

Date: 06/14/2018

Schedule of face-to-face sessions

The following schedule depicts the number of face-to-face sessions according to the “normal” protocol, not counting with the exceptions, ie, patient who can proceed to the following Phases earlier.

Table 4. Face-to-face session schedule

	Weeks	Conventional PT	Experimental
Immediate Post-op Phase	1	0	0
	2	0	0
Phase 1 - Immobilization Weeks 3 to 4	3	2	1
	4	2	1
Total Phase (accumulated)		4 Sessions (4)	2 Sessions (2)
Phase 2 - PROM Weeks 5 to 9	5	3	2
	6	3	2
	7	3	2
	8	3	2
	9	3	1
Total Phase (accumulated)		15 Sessions (19)	9 Sessions (11)
Phase 3 – AROM Weeks 10 to 14	10	3	1
	11	3	1
	12	3	1
	13	3	1
	14	3	1
Total Phase (accumulated)		15 Sessions (34)	5 Sessions (16)
Phase 4 – Strength Weeks 15 to 20	15	3	1
	16	3	0
	17	3	1
	18	3	0
	19	3	1
	20	3	0
Total Phase (accumulated)		18 Sessions (52)	3 Sessions (19)

15. Safety and adverse events

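### The only outcome analysis is an undefined per-protocol set, with no all-randomised analysis or missing-data method beside it in a trial sized for non-inferiority

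*Combined protocol and SAP*

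**What the plan says.** Section 16 (Statistical analysis) gives one population for outcomes: "Outcome analysis will be performed using a per-protocol analysis". Two analyses follow: a two-group t test or Mann-Whitney test on change from baseline to week 20, and a repeated-measures ANOVA. Neither names another population. The section does not say who belongs to the per-protocol set, how a missing week-20 value is handled, or what is done with patients who leave it. Allocated patients are mentioned only for the comparison of baseline characteristics.

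Section 6 (Sample size estimate) bases the calculation on "a non-inferiority scenario", with "a two-sided 0.05 significance level and a 10% dropout rate". Section 2 states the hypothesis that outcomes will be at least similar to those of traditional rehabilitation.

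Section 14 (Intervention) sets no minimum adherence. For device sessions, "compliance to that frequency is not mandatory per protocol". For the control arm's unsupervised sessions, "Compliance to these additional sessions is not mandatory".

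Section 12 (Blinding) has outcomes assessed, and the statistical analysis done, blind to group. Patients are not blinded to their group.

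**The concern.** A per-protocol analysis compares the patients left after selections made since randomisation. If those selections differ between arms and are related to outcome, the groups are no longer comparable. In a non-inferiority trial the resulting shift can make a worse treatment look acceptable, or an acceptable one look worse. The usual safeguard is a second analysis of everyone randomised, so that disagreement between the two is visible. This plan has none. The 10% dropout allowance protects the number of patients, not the comparison. The repeated-measures ANOVA does not fill the gap: it names no other population, and in its conventional form it needs complete data.

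Because the set is undefined, two analysts could build different sets from the same data in good faith. The primary conclusion would then rest on a choice that the document does not fix.

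**Working it through.** **The plan's own figure.** Section 6 gives SD 12.0 (a baseline SD from a cited trial), difference 10.4, 90% power, two-sided 0.05 and 10% dropout.
- Normal approximation: n = 2 × 12² × (1.960 + 1.282)² / 10.4² = 28.0, so 28 per arm. 28/0.9 rounds up to 32 per arm, 64 in all.
- Noncentral t: 29 per arm. 29/0.9 rounds up to 33 per arm, 66 in all.
- With a Mann-Whitney efficiency allowance: 28/0.955 rounds up to 30, and 30/0.9 rounds up to 34 per arm, 68 in all.

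The last route matches the stated 68. The document does not say which route was used. The sample size is not in dispute, and 34 per arm is used below.

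**Illustration of bias.** Assumptions: margin 10.4 (section 6 calls it an MCID, not a margin); SD 12; one-sided 0.025; true difference among all randomised patients exactly at the margin. Ten per cent of one arm is removed, borrowing the dropout figure of section 6, which leaves 30.6. D is the number of points by which removed patients are worse than kept ones; negative D means better. The documents give no value for D.

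Removing 10% of the experimental arm raises its mean by 0.1 × D. Then:
- SE = 12 × √(1/30.6 + 1/34) = 2.990; df = 62.6; critical t = 1.9986.
- Noncentrality = 0.1 × D / 2.990, which is 0.334 at D = 10.

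| Removed | D = −10 | −5 | 0 | 5 | 10 |
|---|---|---|---|---|---|
| 10% of experimental only | 1.1% | 1.7% | 2.5% | 3.6% | 5.1% |
| 10% of control only | 5.1% | 3.6% | 2.5% | 1.7% | 1.1% |

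Entries are false non-inferiority rates. With 10% removed from the experimental arm and 5% from control, the shift is 0.05 × D and the rate is 3.0% at D = 5 and 3.6% at D = 10. With 10% removed from both arms and the same D, the shifts cancel and the rate is 2.5%. For scale, D = 10 moves the estimate by 1.0 point, against a 95% confidence interval half-width of 1.9986 × 2.990 = 6.0 points.

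**Power at a true difference of 0.** With 34 and 34 analysed: 94.1%. With 10% of controls removed: 92.8% at D = 0, 90.3% at D = 5 and 87.2% at D = 10.

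**Cost of requiring two analyses.** Simulation, 34 per arm, true difference 0, removal unrelated to outcome, all week-20 outcomes known:

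| Removed per arm | Per-protocol alone | All randomised alone | Both required |
|---|---|---|---|
| 3 | 91.9% | 94.1% | 91.1% |
| 6 | 89.0% | 94.1% | 88.2% |

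**The case against.** Per-protocol analysis is accepted for a non-inferiority aim, assessors and analyst are blinded, and the set may simply mean patients who finish the programme with week-20 data. The first two points stand, and blinding does limit selective construction of the set. It does not bring removed patients back. The completer reading is not written down, and if it were, there would still be no all-randomised analysis and no missing-data method.

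Three stronger readings are tempting but not supported.
- A reader might infer that membership depends on face-to-face attendance, scheduled at 52 sessions against 19, and so favours the device arm. Nothing ties the set to those counts. The schedule is described as "not counting with the exceptions, ie, patient who can proceed to the following Phases earlier", and a note after Table 5 says "may be less if patient is progressing well", so lower counts are permitted and go with good progress. If low counts did lead to exclusion, better responders would be lost. In the experimental arm that works against a false claim (1.7% or 1.1% above); in the control arm it would do the reverse.
- A reader might conclude that the false-claim rate doubles. That needs loss in one arm only, none in the other, and removed patients about a whole MCID different in the unfavourable direction. The documents give none of these.
- A reader might credit the added analysis with full correction. In simulation with 3 experimental patients removed and D = 10, requiring both analyses lowers false non-inferiority from 4.8% to 2.3%, but only because every outcome was taken as known. That describes patients excluded yet still assessed, not true dropouts.

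It is also fair to say that making the all-randomised analysis primary is a design preference. Having it beside the per-protocol analysis is what matters.

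**Conclusion.** The point holds: an undefined per-protocol set is the sole basis for the outcome conclusions, and nothing planned would show whether exclusions were uneven and related to outcome. This governs the primary conclusion and cannot be credibly repaired after unblinding.

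The documents do not establish that the result will be biased, or in which direction. The 1.1% to 5.1% range rests on an assumed margin, a baseline SD standing in for the SD of change, a borrowed 10% and an assumed D. The 10% is a dropout allowance, not a limit on exclusions from an undefined set. The error rates also presuppose a non-inferiority test, whereas section 16 contains only difference tests, with no margin or confidence-interval rule.

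**What to change.** In section 16:
1. Add an analysis of all randomised patients as allocated, beside the per-protocol analysis: a likelihood-based mixed model on the 6, 12, 16 and 20-week visits, with baseline as covariate and the week-20 contrast. State that patients who stop treatment continue to be assessed.
2. Define the per-protocol set before unblinding, with the same rules in both arms. State that what the protocol already permits (early progression, reduced sessions, omitted non-mandatory sessions) is not a deviation.
3. State the non-inferiority margin, judge it by the two-sided 95% confidence interval in both analyses, and claim non-inferiority only if they agree.
4. Add a sensitivity analysis for missing week-20 data. For true dropouts the mixed model recovers only what earlier visits predict, and essentially nothing for a patient with no postoperative visit.

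The cost is one more main analysis, its sensitivity analysis and some extra follow-up visits. Requiring both analyses costs 0.8 points of power against per-protocol alone in each simulated case (91.9% to 91.1%; 89.0% to 88.2%), and 3.0 to 5.9 points against an all-randomised analysis alone. The all-randomised estimate can be diluted by non-adherence, which is why a defined per-protocol set stays beside it. The planned 68 need not change on this account.

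Separately, and minor: the text of section 14 gives controls three physiotherapist sessions a week, while Table 2 and the face-to-face schedule give two in weeks 3 and 4. These passages must be reconciled.
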